6.3 Study Schematic Diagram

The flow diagram depicting an overview of the trial is presented in Figure 1.

[figure not shown]

Figure 1. Flow diagram for EASY study

6.4 Study Timelines

The overall duration of the study is 42 months. Details of specific trial tasks and planned timelines are presented in Table 3.

Table 3. Study timeline and key tasks

Phase	PHASE 1																																										PHASE 2						PHASE 3																							
	Milestones																																										Internal Pilot						Main Trial																		Analysis & Reporting					
	Pre Grant																																										Set Up						Year 2																		Year 4					
	Year																																										Year 1						Year 3																		Year 4					
Quarter	Q1																																										Q2						Q3																		Q4					
Project Month	-3	-2	-1	1	2	3	4	5	6	7	8	9	10	11	12	13	14	15	16	17	18	19	20	21	22	23	24	25	26	27	28	29	30	31	32	33	34	35	36	37	38	39	40	41	42																											
Calendar Month	Feb-23	Mar-23	Apr-23	May-23	Jun-23	Jul-23	Aug-23	Sep-23	Oct-23	Nov-23	Dec-23	Jan-24	Feb-24	Mar-24	Apr-24	May-24	Jun-24	Jul-24	Aug-24	Sep-24	Oct-24	Nov-24	Dec-24	Jan-25	Feb-25	Mar-25	Apr-25	May-25	Jun-25	Jul-25	Aug-25	Sep-25	Oct-25	Nov-25	Dec-25	Jan-26	Feb-26	Mar-26	Apr-26	May-26	Jun-26	Jul-26	Aug-26	Sep-26	Oct-26																											
Trial Set Up	x	x	x																																																																					
Trial Staff Recruitment	x	x	x	x	x	x	x	x	x	x	x	x	x	x	x																																																									
Protocol Development	x	x	x	x	x	x																																																																		
REC Approval																																																																								
HRA Approval																																																																								
R&D Approval																																																																								
Site Set Up and Training																																																																								
Internal Pilot Study																																																																								
Main Study																																																																								
Sites Initiated/Open to Recruitment																																																																								
Patient Recruitment/Month/Site																																																																								
Patient Recruitment/Month																																																																								
Patient Recruitment Cumulative																																																																								
Data Collection/Cleaning																																																																								
Internal Pilot Review																																																																								
TMG Meetings	x	x	x	x	x	x	x	x	x	x	x	x	x	x	x	x	x	x	x	x	x	x	x	x	x	x	x	x	x	x	x	x	x	x	x	x	x	x	x	x	x	x	x	x	x	x	x	x	x	x	x																					
DMEC Meetings																																																																								
TSC Meetings																																																																								
PPIE Advisory Group																																																																								
Site Closure																																																																								
Statistical Analysis																																																																								
Health Economics Analysis																																																																								
Reporting and Dissemination																																																																								

Abbreviations: REC = Research Ethics Committee; MHRA = Medicines and Healthcare products Regulatory Agency; HRA = Health Research Authority; R&D = Research and Development; TMG = Trial Management Group; TSC = Trial Steering Committee; DMEC = Data Monitoring and Ethics Committee; PPIE = Patient and Public Involvement and Engagement

6.5 End of Study

The trial will end when all participants have completed their 28 day follow-up and database lock occurs. The trial will be stopped early if:

- Mandated by the Research Ethics Committee
- Mandated by the Medicines and Healthcare products Regulatory Agency
- Mandated by the Sponsor e.g. following recommendations from the DMEC
- Funding ceases

The REC that originally gave a favourable opinion of the trial and the MHRA who issued the clinical trial authorisation will be notified in writing if the trial has been concluded or stopped early.

7 TRIAL SETTING AND PARTICIPANT ELIGIBILITY CRITERIA

7.1 Trial Setting

Recruitment for the trial will take place in at least 18 paediatric emergency departments (EDs) and assessment units from across the UK, from within the Paediatric Research in the UK and Ireland (PERUKI) research network and the General and Adolescent Paediatric Research in the United Kingdom & Ireland (GAPRUKI) research network. Sites will be selected based on a wide geographical spread and they must provide evidence that they have:

- Access to the target population
- Local PI willing to lead the trial at that site and a local trial team
- A proven track record of participating in research
- Availability of either point-of-care urinalysis or laboratory microscopy 24 hours a day
- Access to laboratory testing for full blood count, C-reactive protein, creatinine 24 hours a day
- Ability to dispense trial medications 24 hours a day
- Ability to provide a dedicated phone number that can be accessed by parents/guardians between 8am and 8pm 7 days a week
- Ability to provide a departmental phone number that can be accessed by parents/guardians outside of these times

Staff must also comply with the protocol, standard operating procedures (SOPs), the principles of Good Clinical Practice (GCP), regulatory requirements, and be prepared to participate in appropriate trial training. Training will be provided to sites who participate in the study. A list of study sites will be maintained in the TMF.

7.2 Trial Population

Participants will be screened from attendances to paediatric EDs and assessment units at recruiting sites. All participants who meet the study inclusion criteria will be entered into a screening log. If the participant is not recruited the reason will be recorded. This information is required to ensure the study can be reported in keeping with Consolidated Standards of Reporting Trials (CONSORT) guidelines (www.consort-statement.org).

7.3 Eligibility Criteria

Participants will be assessed using the inclusion and exclusion criteria set out below. Eligibility to participate in the trial will be confirmed by a physician who is named on the Delegation Log. The medical care given to, and medical decisions made on behalf of, trial participants will be the responsibility of an appropriately qualified treating physician. Participants will be eligible to participate in the study in accordance with the following criteria:

7.3.1 Inclusion Criteria

1. 29 to 90 days of age (Infants from their 29th day of life to their 90th day of life inclusive. Day of birth is day 1 of life)
2. Suspected urinary tract infection (UTI) requiring treatment with antibiotics
3. History of fever as defined as temperature $\geq 38^{\circ}\text{C}$ measured by any method OR likely fever in last 24 hours including subjective fever reported by caregiver

4. Abnormal urinalysis defined as: (1) abnormal urinary dipstick test (leucocyte esterase $\geq 1+$, or nitrite \geq Trace) OR (2) abnormal urine microscopy (≥ 5 white cells per high-power field in centrifuged urine or ≥ 10 white cells per mm³ in un-centrifuged urine or bacteriuria with any bacteria per high power field)
5. Well on global clinical assessment using the paediatric assessment triangle* assessed by a consultant grade doctor. [28]

***Paediatric Assessment Triangle (appendix 1):**

Normal **Appearance** defined as having a normal cry, good muscle tone and alert. Normal **Circulation** defined as normal colour, heart rate less than 160 beats per minute and a central capillary refill time of less than three seconds. Normal **Work of breathing** defined as regular breathing without excessive respiratory muscle effort and RR < 60 breaths per minute.

7.3.2 Exclusion Criteria

1. Born at < 30 weeks gestation
2. Discharged from hospital more than 7 days after birth
3. Required re-admission to hospital after birth for more than 24 hours
4. Known or suspected structural renal abnormality
5. Evidence of sepsis and/or meningitis (appear unwell, shock, hypotension, altered mental state, bulging fontanelle, lumbar puncture suggestive of bacterial meningitis)
6. Received vaccination within 48 hours of attendance
7. Sodium < 128 mmol/l on lab or blood gas sample
8. Potassium > 6.5 mmol/l on lab sample
9. Plasma creatinine > 50 micromol/l
10. Inability to tolerate oral medication
11. Urine sample was not sent for culture
12. Received additional antibiotics (with the exception of the parenteral antibiotic administered within 24 hours of hospital attendance)
13. Declined consent for participation

7.3.3 Co-enrolment Guidelines

Participants in the EASY study may be eligible for co-enrolment in other studies, and this will be decided on a case-by-case basis by the Trial Management Group. Participants enrolled in other investigational drug studies are not candidates for this study. Participants enrolled in other observational studies are potential candidates for this study. Co-enrolment with other studies should be documented in the Case Report Form (CRF).

8 TRIAL INTERVENTIONS

8.1 Study Intervention and Comparator (standard care)

When a febrile infant (under three months of age) attends hospital they should undergo blood and urine testing and may receive broad-spectrum parenteral antibiotics in the EDs or assessment unit pending laboratory results. This initial hospital assessment will be unaffected by the EASY study.

Clinicians will be free to perform investigations and administer parenteral antibiotics (standard care) during that initial assessment without delay.

Administration of initial parenteral antibiotics, if required based on national clinical guidelines and local policy, should not be delayed pending consent discussions.

Screening should occur once initial laboratory results are known and only eligible “low risk” infants will be invited to participate in the trial.

Randomisation must occur within 24 hours of hospital attendance.

Eligible “low risk” participants will be randomised in a 1:1 ratio to one of two treatment groups.

Intervention: Oral antibiotics and continuation of oral treatment at least until urine culture results are known (typically after 36 to 48 hours).

Comparator: Continuation of parenteral antibiotics (standard care) at least until urine culture results are known (typically after 36 to 48 hours).

Section 9 of the protocol, outlines the oral and parenteral antibiotics to be used in the EASY study.

8.2 Assignment of Intervention

8.2.1 Sequence Generation

Participants will be randomised using an automated web-based or telephone system via randomly permuted blocks in a 1:1 ratio. There will be stratification by recruitment site, sex, age (29-60 days/61-90 days) and antibiotic use.

8.2.2 Allocation Concealment Mechanism

The randomisation sequence will be saved in a restricted section of the TMF, which can only be accessed by the trial statistician and not those who enrol or assign interventions.

8.2.3 Allocation Implementation

After informed consent, participants will be randomised via an automated web-based or telephone system. Sites will be provided with trial specific randomisation guidelines. Randomisation will be completed by an appropriately trained and delegated member of the research team. Each participant will be allocated their own unique Participant Study Number during the randomisation process, which will be used throughout the study for participant identification on all data collection forms and questionnaires. An entry will be recorded in the participants’ medical notes noting enrolment into the study.

8.2.4 Blinding

This study will be a randomised, open label, unblinded trial. Parents/guardians, those who provide health care to the participants, and outcome assessors, will not be blinded to the allocated intervention in this trial. This reflects the pragmatic design focused on clinical effectiveness; it also permits realistic evaluation of the effect of the intervention on hospital admission to take account of admission for reasons other than parenteral antibiotic administration.

The trial statistician, who has no role in decision-making with regards the conduct of the trial, will be unblinded and this will also facilitate linkage with the DMEC. The remainder of the trial team will also be unblinded for the purposes of managing data collection, reviewing cases to assess protocol deviations, and to undertake pharmacovigilance duties.

9 STUDY INVESTIGATIONAL MEDICINAL PRODUCTS

9.1 Safety Considerations of the Intervention

Parenteral antibiotics are routinely given in standard clinical practice to treat suspected UTI until urine culture results are known. In the EASY study we are investigating the use of oral antibiotics pending urine culture results. The safety profile and efficacy of parenteral and oral antibiotics are well established and as they will be used in accordance with their marketing authorisations, the EASY study has been categorised as a Type A Clinical Trial of an Investigational Medicinal Product (CTIMP) study. As the risks are no higher than standard care, a risk-adapted approach to the management of the parenteral and oral antibiotics as investigational medicinal products has been adopted [29].

9.2 Study Drug

The most commonly prescribed oral antibiotics are cephalexin, co-amoxiclav and trimethoprim as outlined in Table 4 and these will be considered as investigational medicinal products (IMP) in the EASY study. These will be used as per the manufacturer's authorisation and within their licensed range of indications, dosage, and form (according to the Summary of Product Characteristics (SPC)).

As in standard clinical practice, if the baby is sick within 30 minutes of administration of any doses of cephalexin, co-amoxiclav or trimethoprim, the dose should be repeated. If this occurs after 30 minutes, the dose should not be repeated and the oral antibiotic should be administered at the next scheduled dosing time. If the baby is sick within 30 minutes for 2 consecutive doses, the clinician should consider whether the oral antibiotic cannot be tolerated.

Table 4. Oral Antibiotics

Oral Antibiotics	
Cefalexin	Licensed oral formulations used in accordance with standard care practice at participating sites
Co-amoxiclav	
Trimethoprim	

The most commonly prescribed parenteral antibiotics are ceftriaxone, cefotaxime, gentamicin, amoxicillin, cefuroxime and co-amoxiclav as outlined in Table 5 and these will be considered as investigational medicinal products (IMP) in the EASY study. These will be used as per the manufacturer's authorisation and within their licensed range of indications, dosage, and form (according to the Summary of Product Characteristics (SPC)).

Table 5. Parenteral Antibiotics

Parenteral Antibiotics	
Ceftriaxone	Licensed parenteral formulations used in accordance with standard care practice at participating sites
Cefotaxime	
Gentamicin	
Amoxicillin	
Cefuroxime	
Co-amoxiclav	

9.3 Study Drug Storage

Study drug will be stored in accordance with manufacturer's recommendations and local practice.

9.4 Study Drug Prescribing, Labelling and Dispensing

When a participant is recruited a member of the research team will use the randomisation service to obtain the unique Participant Study Number and the treatment allocation assigned to the participant. Study drug will be prescribed and dispensed in accordance with usual local site prescription practice. There will be no additional labelling outside the usual practice at local sites. Communication will be given between the research and clinical teams as to which arm of the trial a participant has been randomised to, and participant enrolment into the trial and treatment allocation will be recorded in the clinical notes.

9.5 Study Drug Accountability

There will be no additional records of accountability for supply, administration or destruction of study drug outside the standard clinical practice for these products at the local hospital site.

9.6 Study Drug Administration

Oral and parenteral antibiotics will be given as per locally determined scheduled prescription.

9.7 Study Drug Termination Criteria

Antibiotic treatment may be ended or switched based on clinical assessment during admission or at dedicated telephone reviews. The study drug may also be terminated once urine culture results are known and if no longer clinically indicated.

9.8 Study Drug Adherence

Inpatient administration will be recorded in the hospital prescription chart. Post discharge from hospital, parents/guardians will be verbally asked about adherence at the follow up time points. Any omission of study drug will not be recorded as a protocol deviation.

9.9 Concomitant Care

Paracetamol and ibuprofen can be administered as required to control the infants fever and its associated symptoms. These drugs, and any other concomitant medications, will be recorded on the CRF.

10 OUTCOMES and OUTCOME MEASURES

10.1 Primary Outcome

The primary outcome is treatment failure (i.e. additional parenteral antibiotics) within seven days of randomisation.

Additional parenteral antibiotics in the standard care group is defined as:

- (i) administration of an additional parenteral antibiotic not prescribed as part of initial empirical treatment
- (ii) a change of parenteral antibiotics from standard empirical treatment
- (iii) re-commencing parenteral antibiotics after the decision to terminate parenteral antibiotics.

For the intervention group additional parenteral antibiotics are defined as administering parenteral antibiotics for any reason.

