14 STATISTICAL CONSIDERATIONS

14.1 Sample Size

With a treatment failure rate (i.e. additional parenteral antibiotics within 7 days of randomisation) of 0.5% and a non-inferiority margin of 2%, 524 participants are required based on 90% power and a 1-sided 97.5% Confidence Interval. Of the required population, it is estimated that up to 10% might not provide 7-day follow up. Therefore, a sample size of 584 is needed to obtain the 524 required for analysis.

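### In the standard-care arm any change of parenteral agent counts as failure, whatever the reason, with no oral-arm counterpart. Record reasons and pre-specify an arm-neutral sensitivity analysis.

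*Protocol*

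**What the plan says.** Section 10.1 of the protocol states: "The primary outcome is treatment failure (i.e. additional parenteral antibiotics) within seven days of randomisation". It then defines the event separately by arm.

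- **Standard care.** There are three items. Item (ii), the one at issue here, reads "a change of parenteral antibiotics from standard empirical treatment". The other two are a new parenteral drug beyond the starting regimen (i) and a restart once parenteral treatment had been stopped (iii).
- **Oral arm.** There is a single, broader item: "For the intervention group additional parenteral antibiotics are defined as administering parenteral antibiotics for any reason".

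Item (ii) attaches no clinical reason to the change. Section 9.7 lets clinicians alter treatment in either arm: "Antibiotic treatment may be ended or switched based on clinical assessment during admission or at dedicated telephone reviews". Section 8.1 expects culture results at about 36 to 48 hours, well inside the seven-day window.

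Section 14.1 sizes the trial on a single failure rate of 0.5% and a margin of 2 percentage points. Section 14.2.2 declares non-inferiority when the upper bound of the one-sided 97.5% interval for the risk difference is below that margin.

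**The concern.** The same management decision scores differently by arm. If a control infant is improving and the parenteral drug is changed because of a culture report, or for an administrative reason, item (ii) records a failure. If an oral-arm infant in the same position changes from one oral drug to another, nothing is recorded. Such control events are not failures of treatment, but they lower the oral-minus-control difference and so make non-inferiority easier to declare.

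The counts are small enough for this to matter. At 0.5%, 262 infants yield about 1.3 events (262 × 0.005). One extra control event moves the difference by 1/262 = 0.38 points, about a fifth of the margin.

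Requiring success in both the intention-to-treat and per-protocol analyses (section 14.2.1) does not help, because both use the same event definition. Care is open label and outcome assessors are unblinded (section 8.2.4), so the decisions that generate events are made with the allocation known.

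**Working it through.** **Inputs from the protocol.** Failure rate 0.5%, margin 2 points, one-sided 2.5% level, 90% power, 10% loss (section 14.1); 1:1 allocation (section 8.2.1); decision rule (section 14.2.2).

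**Inputs assumed.** The rates of events that are not failures. The protocol gives none, so a range is shown.

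**1. The plan's own figure.** Per arm, n = [2 × 0.005 × 0.995 × (1.960 + 1.282)²] / 0.02² = 0.00995 × 10.51 / 0.0004 ≈ 261.4, so 262 per arm and 524 in total. Allowing for loss, 262 / 0.9 = 291.1, so 292 per arm and 584 in total. Both stated figures reproduce. The sample-size arithmetic is not in question.

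**2. What one control event can do.** The Wald upper bound is d + 1.96 × √{[p_o(1 − p_o) + p_c(1 − p_c)] / 262}, where d = p_o − p_c. Take three oral failures (3/262):

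| Control failures | Upper bound | Below 2%? |
|---|---|---|
| 0 | 2.43% | no |
| 1 | 2.25% | no |
| 2 | 2.05% | no |
| 3 | 1.82% | yes |

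One control infant whose drug was changed for a reason other than failure can thus turn two control events into three and reverse the conclusion.

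**3. Chance of declaring non-inferiority when oral is truly at the margin (2.5% v 0.5%).** Two calculations are shown. The normal approximation is Φ[(0.02 − d)/SE − 1.96]. The other enumerates all pairs of binomial counts at 262 per arm and applies the Wald rule. Example with 1 point added to controls: d = 0.025 − 0.015 = 0.010; SE = √[(0.025 × 0.975 + 0.015 × 0.985)/262] = 0.01222; Φ(0.818 − 1.960) = Φ(−1.142) = 12.7%.

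| Points added to control | Points added to oral | Normal approx. | Enumerated Wald |
|---|---|---|---|
| 0 | 0 | 2.5% | 5.0% |
| 0.5 | 0 | 6.4% | 8.9% |
| 1.0 | 0 | 12.7% | 15.1% |
| 2.0 | 0 | 31.1% | 33.5% |
| 1.0 | 0.5 | 5.8% | 7.5% |
| 1.0 | 1.0 | 2.5% | 3.5% |

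The enumerated baseline of 5.0% exceeds the nominal 2.5% because the Wald bound is inaccurate at such low counts. That is a separate matter; the effect of the definition is the change from the baseline.

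**4. Is 1 point plausible?** Section 4.2 reports confirmed UTI in 4 of 114 low-risk infants (4%) and in 67 of 555 infants febrile on arrival (12%). If culture-directed changes occurred only in confirmed UTI, a 1% rate would need about one in four such infants to change to another parenteral drug at 4% prevalence, or one in twelve at 12%. Half a point would need one in eight or one in twenty-four. Stopping, or stepping down to oral treatment, is not an item (ii) event. One point is possible, but the document does not establish it.

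**The case against.** Some difference in wording is unavoidable: controls are on parenteral treatment by allocation, so additional parenteral treatment has to be described differently for them. This stands. It does not explain why item (ii) carries no reason.

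A reader might go further and infer that the oral arm's any-reason rule is an equal defect, and that the primary endpoint must be replaced by one reason-based definition. The documents do not support that. The rationale in section 4.2 asks whether oral treatment avoids additional parenteral antibiotics, and for that strategy question any parenteral dose in the oral arm counts against the strategy. The rule is also objective, and it works against a non-inferiority claim. It can cost power: with equal true rates of 0.5%, 1 point of oral-only events cuts enumerated Wald power from 87% to 28%. But that error is a missed claim, not a false one. A reason-based primary endpoint would rest on unblinded clinicians' judgement. Excluding moves to parenteral treatment prompted by resistance to the oral drug could itself favour non-inferiority.

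A reader might also infer that the trial is biased towards non-inferiority on balance. The last two rows of the table show why that cannot be said: events of this kind in both arms largely cancel.

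The secondary escalation-in-care outcome (section 10.2) uses one wording for both arms and gives partial cover, but it does not correct the primary comparison. Table 6 lists post-randomisation antibiotic administration without mentioning reasons. The case report form is not shown, so it cannot be said that reasons go unrecorded.

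**Conclusion.** The point holds for item (ii). It counts changes of agent without a reason, has no counterpart in the oral arm, and where it captures non-failures it pushes towards non-inferiority. Under the assumed rates, with oral treatment truly 2 points worse and no offsetting oral-arm events, 0.5 to 1 point of such control events raises the enumerated chance of a false claim from 5% to between 9% and 15%. Offsetting events bring it to 7.5% or 3.5%. Neither net direction nor net size can be known from the protocol.

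This does not invalidate the primary endpoint or the sample size. It leaves a non-inferiority claim open to a challenge that could not be answered later if reasons had not been captured. It should be fixed, as a cheap improvement.

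**What to change.** 1. Keep the section 10.1 definition as the primary outcome, including the oral arm's any-reason rule.
2. On the post-randomisation antibiotic page of the case report form, record for both arms the reason for every parenteral start, addition, change or restart.
3. Pre-specify an arm-neutral sensitivity analysis of the day-7 and day-28 outcomes in which item (ii) counts only changes made for inadequate response, and death is counted. Run two versions: one still counts every oral-arm parenteral dose; the other applies the same reason rule to both arms.
4. State in advance that a non-inferiority claim will be reported as robust only if it holds when the non-failure control changes are removed.

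The cost is one form field and a short addition to the analysis text. The drawback is that unblinded clinicians judge the reason, which is why this is a sensitivity analysis and not the primary. The field should be added as early as possible, since reasons not recorded at the time may be unrecoverable.
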